11.2.2 Meetings periodicity

A first meeting to present the research project to the Data Safety and Monitoring Board shall be organized at the start of the research if possible, at the initiative of the chairperson of the Scientific Advisory Board. The next meetings are scheduled in an agenda established at the beginning of the inclusions.

Extraordinary meetings may be requested by the chairperson of the Scientific Advisory Board of the research or the Sponsor in case of unexpected or serious issues.

11.2.3 Missions

The mission of the Data Safety and Monitoring Board is to ensure the safety of the participants and to maintain the scientific and ethics integrity of the research project during the whole conduct of the research. This Board has a consultative role for the Scientific Advisory Board and the Sponsor.

The DSMB may help to make, during the conduct of the research, decisions for which an independent judgment is needed. It may give advice in the following circumstances:

- Recommendation on an early trial termination (for toxicity reason or because the trial is not anymore feasible, or because all the elements of conclusion are achieved)
- Recommendation on major protocol modification, regarding enrollment or study follow-up or new scientific data
- Interim analysis: analysis results interpretation, asks for analysis or additional study data.

The written Independent Committee opinion is sent to the sponsor and the Scientific Committee Director. The sponsor shall send the opinion to the Ethics Committee and to the Competent Authorities as part of the safety annual report. A duplicata is sent to the MMC for filing.

The DSMB will review the progress, efficacy, and safety data of this study after the first fifteen patients have completed the treatment period (W8) or prematurely discontinued the study drug.

No formal stopping rules will be used by the DSMB for safety outcomes. Rather, a clinical assessment will be made to determine if the nature, frequency, and severity of adverse events associated with the treatment under investigation warrants the early termination of the study in the best interest of the participants.

11.3 Methodology and Management Centre (MMC)

The sponsor mandates the team of the MMC to manage the study

The project team of the MMC is constituted of a coordinating investigator, a methodologist/biostatistician, a project manager, a data manager and Clinical Research Associates.

The MMC is in charge of the study:

- Performs study set up, the procedure of subjects' enrollment, study data collection and monitoring, the constitution and management of the data base and statistical analysis,
- Coordinates the functioning of the investigation sites (clinical units, hospital pharmacy, virology laboratory),
- Informs the sponsor and the Scientific Committee of the study progression,
- Organises the Scientific Advisory board and general assembly of investigators,
- Actively participates in the communication and the publication of the results.

12 CIRCUIT OF SAMPLES

12.1 Samples for the biological analyses planned by the protocol

Blood samples are constituted at the various study visits to allow the realization of the biological check-up. Biological analyses are performed in real time at recruitment site local laboratories, with respect to the site procedures.

12.2 Biobank

At some study visits (cf. timetable §2), blood samples are drawn to establish biobank constituted of serum and plasma samples.

Samples will be prepared, labelled, anonymised (study patient number) and stored at -80°C according to biobank procedure. This procedure will mention details of the sampling in terms of volume, numbers of drawn tubes as well as the modalities of preparation of each type of sample.

Samples will be collected and stored on each investigator's site.

Biobank samples may be used to verify biological data of the protocol and to perform further researches authorised by the Scientific Advisory Board of the study. This may allow to understand best or to prevent clinical, biological, therapeutic evolution of hepatitis C in co-infected patients.

➤ **The samples of serum and plasma bank will be used to perform the following analyses:**

- Genotypic resistance test if HIV virological failure
- Measure of HCV viral load and genotypic resistance test if HCV virological failure
- Assessment if necessary of ART concentrations

Several complementary virologic studies are considered. They would be performed with stored biobank samples following acceptance by the Scientific Advisory board, and depending on their interest and pertinence based on the evolution of knowledge.

13 STATISTICAL CONSIDERATIONS

13.1 Statistical hypotheses

The main end-point during statistical analysis is defined as SVR12 and its precision, calculated as the 95% Clopper-Pearson confidence interval (CI), with a type I error of 5%.

13.2 Sample size determination

Since the study is single-arm, non-comparative in design, the sample size will be based on statistical precision and not a comparative statistical test. The sample size should allow a precision of <30% absolute difference between lower and upper bounds of the Clopper-Pearson 95%CI. The expected SVR12 rate is 80% from previous studies, hence bounds are calculated from point estimates of SVR12 $\geq 80\%$. A total 30 patients are necessary to fulfill the statistical criteria above.

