The main end-point in statistical analysis is defined as SVR12 and its precision, calculated as the 95% Clopper-Pearson confidence interval (CI). In order to maintain an absolute difference between lower and upper bounds of the 95%CI <30% with an SVR12 \geq 80%, 30 patients need to be included.

• Population analyzed

All patients included in the study, apart from patients who present at least one of the following conditions:

- patients who have never taken treatment,
 - patients who have withdrawn their consent,
 - patients included erroneously with contra-indications to the treatment of the study or without indication to be treated,
- constitute the modified intent-to-treat (ITT) population and will be analyzed.

• Evaluation of the primary endpoint

The main endpoint of the trial is the Sustained Virological Response defined by undetectable plasma HCV RNA (< 12 IU/mL) 12 weeks after cessation of treatment with Grazoprevir / Elbasvir.

- Patients who will be lost to follow-up at PT12 visit and patients who will meet the criteria for interruption of treatment for virological failure will be considered as failures in the analysis of the main endpoint.
- Patients who undergo the treatment up to W8 and with undetectable HCV-RNA at PT12 will be considered as successful
- Patients who stop treatment prematurely for intolerance and with undetectable HCV-RNA at PT12 will be considered as successful.

- Patients who cannot undergo the PT12 visit and with undetectable HCV-RNA at W48 will be considered as successful.

Study timetable

- Trial start date: **May-June 2017**
 - Enrolment period: **12 months**
 - Subject participation duration: screening (1 to 4 weeks before D0), then 56 weeks of follow-up → **approximately 60 weeks maximum**
 - Total trial duration: **24 months**
 - Estimated study completion date: Mid **2019**
-

Schedule of assessments

- Evaluation of inclusion criteria: 1 to 4 weeks
- Anti-HCV treatment: 8 weeks
- Follow up: 48 weeks following the end of the treatment

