13.8 Primary endpoint

The main endpoint of the trial is the Sustained Virological Response defined by undetectable plasma HCV RNA (< 12 IU/mL) 12 weeks after cessation of treatment with Grazoprevir / Elbasvir.

- Patients who will be lost to follow-up at PT12 visit and patients who will meet the criteria for interruption of treatment for virological failure will be considered as failures in the analysis of the main endpoint.
- Patients who undergo the treatment up to W8 and with undetectable HCV-RNA at PT12 will be considered as successful
- Patients who stop treatment prematurely for intolerance and with undetectable HCV-RNA at PT12 will be considered as successful.
- Patients who cannot undergo the PT12 visit and with undetectable HCV-RNA at W48 will be considered as successful.

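### With 30 patients and the planned SVR12 of 80%, the Clopper-Pearson 95% CI is 30.9 points wide, so the plan's <30-point precision claim fails at its own design value

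*Combined protocol and SAP*

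**What the plan says.** Section 13.2 states that "the sample size will be based on statistical precision and not a comparative statistical test". It then sets the target: "The sample size should allow a precision of <30% absolute difference between lower and upper bounds of the Clopper-Pearson 95%CI". The rate at which the target is judged is also given: "The expected SVR12 rate is 80% from previous studies, hence bounds are calculated from point estimates of SVR12" of 80% or more. The section concludes: "A total 30 patients are necessary to fulfill the statistical criteria above".

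The synopsis (statistical hypotheses) repeats the criterion, "In order to maintain an absolute difference between lower and upper bounds of the 95%CI <30% with an SVR12" of at least 80%, and again gives 30 patients. Section 13.1 names the two-sided 95% Clopper-Pearson interval as the measure of precision for the primary endpoint.

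On the denominator, section 13.4 removes three groups from the modified ITT population: patients never treated, patients who withdrew consent, and patients included in error. Under section 13.8, "Patients who will be lost to follow-up at PT12 visit and patients who will meet the criteria for interruption of treatment for virological failure" count as failures, so they stay in the denominator. Section 13.2 makes no allowance for the section 13.4 exclusions.

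**The concern.** Method, width, rate and sample size are all stated, so the claim can be checked directly. Exact intervals are wider than the usual approximate ones, and a width just under 30 points at 80% with 30 patients looked like the result of a different interval method.

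The trial is single-arm and has no hypothesis test, margin or power statement. The interval width is therefore the only statistical property offered in support of 30 patients. If it does not hold at the rate the trial was planned on, anyone who reads section 13.2 is told the estimate will be more precise than it may be. If 24 of 30 patients respond, the primary report will show an interval that contradicts the protocol.

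**Working it through.** **Inputs**

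- Interval: Clopper-Pearson, two-sided 95% (sections 13.1 and 13.2, synopsis).
- Target: upper bound minus lower bound strictly below 30 percentage points (section 13.2, synopsis).
- Rate: observed SVR12 of 80% or more, with 80% expected (section 13.2). The value 80% is inside the range.
- Sample size: 30 (section 13.2, synopsis).

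**Formula.** For x responders among n patients:

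- lower = 2.5% quantile of Beta(x, n − x + 1)
- upper = 97.5% quantile of Beta(x + 1, n − x)

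**The plan's own case, n = 30.** At exactly 80%, x = 0.80 × 30 = 24. The limits come from Beta(24, 7) and Beta(25, 6).

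| Responders | SVR12 | 95% CI | Width (points) | <30? |
|---|---|---|---|---|
| 24/30 | 80.0% | 61.43% to 92.29% | 30.85 | no |
| 25/30 | 83.3% | 65.28% to 94.36% | 29.08 | yes |
| 26/30 | 86.7% | 69.28% to 96.24% | 26.97 | yes |
| 27/30 | 90.0% | 73.47% to 97.89% | 24.42 | yes |

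Widths are taken from unrounded limits. They keep falling from 28/30 to 30/30. The plan's figure is therefore not reproduced at 80%.

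**Could another method explain it?** At n = 30 and 80%, the widths are Wald 28.6, Agresti-Coull 28.5, Jeffreys 27.9 and Wilson 27.8 points. A 90% Clopper-Pearson interval gives 26.6. Each of these would meet the target, but none is the interval that the plan names.

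**Chance of meeting the target with n = 30**

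- True SVR12 80%: P(X ≥ 25) = 0.428. The expected width is 30.15 points.
- True SVR12 85%: P(X ≥ 25) = 0.711.
- True SVR12 90%: P(X ≥ 25) = 0.927.

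**Which n would meet the criterion?** The table gives the widest interval over all attainable counts with x/n ≥ 0.80.

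| n | Lowest count ≥80% | Width (points) | <30? |
|---|---|---|---|
| 27 | 22 (81.5%) | 31.78 | no |
| 28 | 23 (82.1%) | 30.83 | no |
| 29 | 24 (82.8%) | 29.93 | yes |
| 30 | 24 (80.0%) | 30.85 | no |
| 31 | 25 (80.6%) | 30.02 | no |
| 32 | 26 (81.3%) | 29.23 | yes |

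From 32 upward every n checked (to 49) meets the target. The value n = 29 passes only because its lowest attainable rate is 82.8%. Interpolated to exactly 80% its width is 31.4 points, and on that basis the width first falls below 30 at n = 32 (29.85, against 30.34 at n = 31).

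**If fewer than 30 are analysed.** With 28 analysed, the target needs at least 24 responders, since 23/28 fails. At a true rate of 80%, P(X ≥ 24) = 0.315.

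**The case against.** The strongest reply concerns size. The miss is 0.85 points, and among outcomes of 80% or more with 30 patients only 24/30 misses. This is a non-comparative pilot. No test, success threshold or stopping rule uses the 30-point width, and the report will show the actual interval whatever its width, so neither the estimate nor its interval is biased. All of this stands, and it limits what is at stake.

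A second reply is that the 43% is unconditional. It counts outcomes of 23/30 or fewer as misses (probability 0.393 at a true rate of 80%), although the plan promises nothing for those. Restricted to outcomes of at least 24/30, the target is met with probability 0.428 / 0.607 = 0.70, and the one failing outcome, 24/30, has probability 0.179. That is a fair reading aid. The 43% is correct for the question it answers, namely how often a trial with a true rate of 80% would deliver the stated width.

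Third, exclusions from the modified ITT population are possible, not certain. Patients lost to follow-up stay in the denominator, and dropping to 29 does not break the criterion. This also stands. It affects the side point about the analysed number and leaves the result at 30 untouched.

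Finally, the amendment log links the reduction to 30 patients to recruitment. That may explain why 30 was chosen, but it does not make the precision statement true.

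**Conclusion.** The concern holds. Under the interval method, target, rate and sample size that the plan itself states, the width at 80% is 30.85 points and the <30-point claim is false there. It becomes true from 25/30 upward. Nothing elsewhere in the document corrects it.

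The error is about 1 point and affects the stated precision only. The conclusion rests on reading the target as the full width and on including 80% in the range, and section 13.2 says both. The 43% additionally assumes a true SVR12 of 80% and 30 analysed patients.

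**What to change.** Replace the precision statement in section 13.2 and in the synopsis with wording such as:

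> Thirty analysed patients give a Clopper-Pearson 95% CI no wider than 31 points for any observed SVR12 of 80% or more (24/30: 61.4% to 92.3%), and narrower than 30 points when at least 25 of 30 (83.3%) respond.

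Optionally, add one line with the widths at the lowest count of 80% or more if exclusions reduce the analysed number: 29.9 points at 29, 30.8 at 28 and 31.8 at 27.

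The cost is two sentences, and the stated precision becomes about 1 point less favourable. Enrolment, design and analysis do not change. If the sponsor prefers to keep the <30-point claim as written, it would need at least 32 analysed patients.

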13.3 Statistical methods

- **Qualitative variables**

Qualitative variables will be described in terms of numbers of patients, percentages and confidence intervals.

- **Quantitative variables**

Quantitative variables will be described in terms of populations, medians, range and interquartile range or means, standard deviations and confidence intervals of the mean.

- **Variables of the type 'Time to onset of an event'**

The risk of the first onset of events of interest will be described in terms of probability of onset and confidence intervals with the Kaplan-Meier method. The date of origin is the date of inclusion in the research and the time to onset is the difference between the date of diagnosis of the event and the date of inclusion.

A graphic representation will be associated with the results of the analyses whenever possible.

- **Software used for the statistical analysis**

The analyses will be done using STATA® software for usual statistical analyses.

13.4 Population analysed

All patients included in the study, apart from patients who present at least one of the following conditions:

- patients who have never taken treatment,
- patients who have withdrawn their consent,
- patients included erroneously with contra-indications to the treatment of the study or without indication to be treated,

constitute the modified intent-to-treat (ITT) population and will be analysed.

Deceased patients and patients lost to follow-up will be included in the analysis until the time of their death/last news.

The decision to exclude a patient from the analysis is made jointly with the Scientific Advisory Board following the recommendations of the independent committee after the collection of the data by the Methodology and Management Centre, without knowing the evolution of the patient after inclusion.

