8.2.3 Description of selected adverse reactions

Laboratory abnormalities

- *Serum ALT elevations*

During clinical trials with the study treatment (with or without ribavirin), regardless of treatment duration, $< 1\%$ (13/1690) of subjects experienced elevations of ALT from normal levels to greater than 5 times the ULN, generally at or after treatment week 8 (mean onset time 10 weeks, range 6-12 weeks). Most ALT elevations resolved with ongoing therapy with the study treatment or after completion of therapy. The frequency of ALT elevations was higher in subjects with higher grazoprevir plasma concentration. The incidence of late ALT elevations was not affected by treatment duration. Cirrhosis was not a risk factor for ALT elevations.

- *Serum Bilirubin Elevations*

During clinical trials with the study treatment (with or without ribavirin), regardless of treatment duration, elevations in bilirubin at greater than 2.5 times ULN were observed in 6% of subjects receiving the study treatment with ribavirin compared to $< 1\%$ in those receiving the study treatment alone. These bilirubin increases were predominantly indirect bilirubin and were generally observed in association with ribavirin co-administration. Bilirubin elevations were typically not associated with serum ALT elevations.

- *Decreased Hemoglobin*

During clinical trials with the study treatment (with or without ribavirin), the mean change from baseline in hemoglobin levels in subjects treated with the study treatment for 12 weeks was -0.19 mmol/L (-0.3 g/dL) and with the study treatment with ribavirin for 16 weeks was approximately -1.37 mmol/L (-2.2 g/dL). Hemoglobin declined during the first 8 weeks of treatment, remained low during the remainder of treatment, and normalized to baseline levels during follow-up. Less than 1% of subjects treated with the study treatment with ribavirin had hemoglobin levels decrease to less than 5.28 mmol/L (8.5 g/dL) during treatment. No subjects treated with the study treatment alone had a hemoglobin level less than 5.28 mmol/L (8.5 g/dL)

Adverse reactions in subjects with HCV/HIV-1 co-infection

The type and severity of adverse reactions in subjects with HCV/HIV-1 co-infection (n=298) were comparable to subjects without HCV/HIV-1 co-infection.

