13.9 Secondary endpoints

HCV virological assessment

- Median (+IQR) of log HCV RNA at W4, W8, PT4 and PT12, globally and according to genotypes.
- Rate of HCV RNA (<12 IU/mL) at W4, W8, PT4 and PT12, globally and according to genotypes.
- Odds ratio of factors associated with SVR12.
- Number of HCV (NS5A and NS3/4) resistance mutations in patients with virological failure.
- Rate of adherence and quality of life measured by specific scales using self questionnaires.
- Number of patients with positive HCV RNA per hundred months follow-up.

HIV virological assessment

- Median (+IQR) of log HIV RNA at D0 and PT12
- Median (+IQR) of CD4 and CD8 cell counts (absolute count, percentage and CD4/CD8 ratio) at D0 and PT12.
- Number of AIDS-defining clinical or biological events using CDC classification (95% CI).

Safety assessment

- Number of adverse clinical and biological events that occur during the treatment and up to 48 weeks after the end of the treatment (95% CI).

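### The only analysis population drops some treated patients who were enrolled in error, and the safety endpoint has no population of its own, so their adverse events fall outside the planned safety counts

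*Combined protocol and SAP*

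**What the plan says.** Section 13.4 starts from all included patients and takes away three groups: "patients who have never taken treatment", "patients who have withdrawn their consent", and "patients included erroneously with contra-indications to the treatment of the study or without indication to be treated". Those who remain "constitute the modified intent-to-treat (ITT) population and will be analysed". The synopsis repeats the definition. No safety, all-treated or per-protocol set is defined; per-protocol appears only in the abbreviation list.

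On who decides, 13.4 says that "The decision to exclude a patient from the analysis is made jointly with the Scientific Advisory Board", on the advice of the independent committee and blind to the patient's course after inclusion. It refers to the analysis as a whole and does not limit the exclusion to efficacy.

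Section 13.9 gives the safety endpoint as "Number of adverse clinical and biological events that occur during the treatment and up to 48 weeks after the end of the treatment", with a 95% CI and no population. The safety objective in the synopsis covers all clinical and biological events during the study.

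**The concern.** Leaving out wrongly enrolled patients can be defended for a response rate, where the question is how the regimen performs in the intended patients. It does not suit a safety summary, whose natural denominator is everyone exposed to the drug. With no safety set, the efficacy-style exclusion carries over to the adverse event endpoint by default.

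At stake is whether the reported safety table describes all exposed patients. In a pilot of 30, one or two omitted patients can decide whether an uncommon event is reported as seen or as not seen. Events that follow an enrolment error are also information that a reader would expect to find in that table.

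**Working it through.** **Step 1. Whom does the exclusion affect?** Never-treated patients are already removed by their own item in 13.4. The erroneous-inclusion item therefore changes the population only by removing patients who took at least one dose. It has two limbs: a contraindication to study treatment, and no indication to be treated.

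**Step 2. Does the safety endpoint escape it?** The places to look are these:
- 13.4 and the synopsis: one population, said to be what is analysed.
- 13.9: safety endpoint, no population named.
- 13.6: eligibility violations are presented, but as baseline description and not as adverse events.
- 10.2.2: serious and non-serious events are collected from consent to 30 days after treatment, with no eligibility condition.
- 10.3.2.3: the annual safety report tabulates all SAEs and SARs. It does not cover non-serious events and does not supply the 13.9 endpoint.

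The data will exist, but the only stated analysis rule leaves them out.

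**Step 3. Check of the interval method on the plan's own figure.** The plan gives no figure for this point. Its one related figure is N = 30, for a Clopper-Pearson 95% CI narrower than 30 points at SVR12 of at least 80% (13.2). Taking the smallest whole count that reaches 80%, the criterion is first met at N = 29 (24/29, width 29.9 points). It is narrowly missed at 30 (24/30, 61.4% to 92.3%, width 30.9 points) and at 31 (30.02 points), and it holds from 32 to 40, the largest N tried. The stated 30 is thus reproduced to within two patients. Nothing below depends on it.

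**Step 4. Illustration.** Assumptions, none of them from the documents: all 30 planned patients are treated, k of them are excluded as erroneous inclusions, each of the k has the event, and b of the others have it. The documents do not give k. The measure is the proportion of patients with the event. The endpoint is worded as a number of events, so the intervals below only show scale.

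Clopper-Pearson limits for x out of n: lower = Beta quantile at 0.025 with parameters (x, n − x + 1); upper = Beta quantile at 0.975 with parameters (x + 1, n − x). For x = 0 the lower limit is 0 and the upper is 1 − 0.025^(1/n). With n = 29: 1 − 0.025^(1/29) = 0.1194.

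| k | b | Modified ITT, as planned | All treated |
|---|---|---|---|
| 1 | 0 | 0/29 = 0% (0 to 11.9%) | 1/30 = 3.3% (0.1 to 17.2%) |
| 2 | 0 | 0/28 = 0% (0 to 12.3%) | 2/30 = 6.7% (0.8 to 22.1%) |
| 1 | 2 | 2/29 = 6.9% (0.9 to 22.8%) | 3/30 = 10.0% (2.1 to 26.5%) |

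**Step 5. Direction.** Removing patients can lower the raw count or leave it unchanged. The rate can move either way. If the one excluded patient has no event and two others do, the modified ITT gives 2/29 = 6.9% against 2/30 = 6.7% among all treated. If k = 0, nothing changes.

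**The case against.** Five points can be made for the plan.

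**The events stay in the trial record.** They are collected under 10.2.2. SAEs, which include grade 4 laboratory events (10.1.3), are notified under 10.2.4 and tabulated in the annual report. The DSMB reviews safety after the first fifteen patients finish or stop treatment, with no stated restriction to the modified ITT (11.2.3). This stands, and it limits the damage to the final statistical summary, mainly for non-serious events. It does not put the events back into the 13.9 counts.

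**Exclusion is decided blind to the patient's course.** This stands too. Patients cannot be removed because they had an event, but the events of those who are removed are still missing.

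**A risk-related bias is not shown.** A reader might infer that the excluded patients are those at highest risk, so that the safety result must be biased downwards. Section 8.2.3 does say "The frequency of ALT elevations was higher in subjects with higher grazoprevir plasma concentration". But the list of contraindicated drugs in 8.2.1 gives no direction of effect on grazoprevir concentration for any item, and it includes enzyme inducers. The no-indication limb has no stated link to risk. Nowhere are patients ranked by risk, so neither inference is supported.

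**The obvious example may not fit.** A reader might also take a patient enrolled on a contraindicated antiretroviral as the typical exclusion. Section 7.2 separates contraindications to the study drugs themselves (criterion 16) from disallowed antiretrovirals (15) and contraindicated co-treatments (17). The 13.4 wording is closest to criterion 16, and the text leaves open whether 15 and 17 are covered. A drug started after inclusion is not an erroneous inclusion.

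**The illustration is a constructed case.** Where b = 0, the excluded patients are assumed to be the only ones with the event. For ALT rises from normal to above 5 × ULN, the rate in 8.2.3 is 13/1690 = 0.8%, or 30 × 13/1690 = 0.23 patients expected in 30. The intervals overlap widely and there is no safety hypothesis to overturn. This stands: the table shows what could happen and is not a forecast.

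**Conclusion.** The point holds as a defect in the stated analysis rule. Followed literally, 13.4 removes exposed patients from the only population that is analysed, and 13.9 gives safety no other. That contradicts the objective of describing all events. The gap concerns the planned safety counts and their 95% CIs, not data collection or expedited reporting.

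Its size depends on how many patients are enrolled in error and treated, and on whether they have events. The documents give neither, so the effect may be zero and its direction on a rate is open. If one of 30 treated patients is such a case and has the only event, the report reads 0/29 (0 to 11.9%) instead of 1/30 (0.1 to 17.2%). SVR12 and the sample size are unaffected. It should be corrected, because the repair costs almost nothing and the present wording gives no basis for reporting these patients' events in the safety analysis.

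**What to change.** - In 13.4 and the synopsis, add a safety population: all patients who took at least one dose of study drug, whatever the eligibility error, subject to section 9.13. That section requires the data of patients who withdraw consent to be deleted unless they authorise their use, so an unqualified all-treated set would conflict with it.
- In 13.9, state that the safety endpoint is analysed in this population.
- List separately the adverse events of patients included in error, with the reason for the error.
- Keep the modified ITT for SVR12 and the other virological endpoints.

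The cost is a few sentences, one listing and one extra denominator in the safety table. No new data are needed, and neither the sample size nor the primary analysis changes. The reported event rate may turn out slightly less favourable.
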